3.3.6 Other Considerations

The following estimands are evaluated for the primary efficacy endpoint (change from baseline in mean sSOL on Month 6) in this study ([Mallinckrodt, et al., 2012](#), and [ICH, E9\(R1\) Final Concept Paper, 2014](#)). The details of the analysis method are discussed in [Section 3.4](#).

Table 4 Estimands

Estimand	Description	Population	Intervention Effect of Interest	Analysis Type
Difference in outcome improvement for all randomized subjects	- all randomized subjects regardless of the treatment subjects actually received - include data after dropout	FAS	missing values imputed using MI assuming MNAR utilizing CCMV missing value pattern (complete cases) (Assumes the probability of missing observations for any subject depends on the unobserved events. For the missing pattern, complete cases will be used in the imputation. Thus this method assumes dropouts or subjects with missing values have similar treatment effect as the completers within the respective treatment group.)	primary
Difference in outcome improvement for all randomized subjects	- all randomized subjects regardless of what treatment subjects actually received - include data after dropout	FAS	missing values imputed using MI assuming MNAR utilizing CCMV-7 missing value pattern (all available up to 7 monotone missing patterns) (Assumes the probability of missing observations for any subject depends on the unobserved events. For the missing pattern, complete cases up to 7 monotone missing patterns will be used in the imputation – see Section 3.4.1.3 for details. Thus this method relaxes the assumption of the primary analysis of using only completers to impute the missing data.)	Sensitivity (CCMV-7)
Difference in outcome improvement for all randomized subjects	- all randomized subjects regardless of what treatment subjects actually received - include data after dropout	FAS	a range of shifts starting from the primary analysis (CCMV) will be used in the multiple imputation of missing data assuming MNAR to identify the specific shift and treatment effect that will tip the results from statistically significant to non-significant	Sensitivity (tipping point)
Difference in outcome improvement for all randomized subjects	- all randomized subjects regardless of the treatment subjects actually received - include data after dropout	FAS	missing values imputed using MMRM model assuming MAR (Assumes subjects with missing values behave the same as the observed data within that treatment group, i.e., the missingness is independent of unobserved data after accounting for the observed data in the model. Thus the dropouts or subjects with missing values may continue to benefit from the treatment as if they were still on treatment (just like completers.))	Supplementary (MMRM analysis assuming MAR)
Difference in outcome improvement for all randomized subjects	- all randomized subjects regardless of the treatment subjects actually received	6-Months Completer Analysis Set	subjects who completed all primary and secondary efficacy assessments without missing visits	Supplementary (completer)

Estimand	Description	Population	Intervention Effect of Interest	Analysis Type
	- subjects who complete the study without missing efficacy assessments			analysis)
Difference in outcome improvement for those who adhere to treatment	- subjects without major protocol violations that would impact efficacy assessments - include data after dropout	PP	missing values imputed using MI assuming MNAR utilizing CCMV missing value pattern (complete cases) (Assumes the probability of missing observations for any subject depends on the unobserved events. For the missing pattern, complete cases will be used in the imputation. Thus this method assumes dropouts or subjects with missing values have similar treatment effect as the completers within the respective treatment group.)	Supplement ary (PP analysis)

FAS = full analysis set; MI = multiple imputation; MAR = missing at random; MMRM = mixed effect model with repeated measurement; MNAR = missing not at random; PP = per-protocol analysis set;

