2 DETERMINATION OF SAMPLE SIZE

The sample size was estimated for the comparison of LEM10 and LEM5 with PBO, with respect to the mean change from Study Baseline at the end of Month 6 of the mean sSOL, the mean sSE and mean sWASO. This estimate was based on a sequential gate-keeping procedure at the 0.05 α -level in Section 3.3.3. There was sufficient power for both the primary endpoint (sSOL) and key secondary endpoints (sSE and sWASO).

On the basis of the dose-finding study E2006-G000-201 (Study 201), across various lemborexant doses (1 to 25 mg) at Days 8 to 15, the standard deviation of change from Study Baseline for sSOL was assumed to be 33 minutes; for sSE was assumed to be 12%; and for sWASO was assumed to be 43 minutes. The LS mean treatment differences at Days 8 to 15 from Study 201 were as follows: for sSE 9.5% for LEM10 and 5.5%, for LEM5; for sWASO -26.6 minutes for LEM10, and -11.3 minutes for LEM5. As a result of the non-normal distribution of sSOL, the LS mean treatment difference is not available (geometric mean ratios were used). Therefore, estimating treatment difference using medians at Days 8 to 15 from Study 201, leads to a median treatment difference of approximately -6.8 minutes for LEM10. For LEM5, a median treatment difference was approximately -13.2 minutes.

To detect a treatment difference in sSOL of at least -8.7 minutes, a sample size of 300 per treatment group at 5% (2-sided) level of significance had >90% power for comparing a dose of lemborexant with PBO.

To detect a treatment difference in sSE of at least 5.5%, a sample size of 300 per treatment group at 5% (2-sided) level of significance had >99% power for comparing a dose of lemborexant with PBO.

For sWASO, a total of 900 subjects (300 per treatment group) gave 90% power to detect a difference of -11.4 minutes for LEM5 and LEM10 compared to PBO (Table 2). The study was adequately powered to show the statistically significant difference from PBO for LEM10 as well as for LEM5.

Table 2 Sample Size Calculations for Study E2006-G000-303

Alpha=0.05	Difference between Active and Placebo CfB (min)	Power = 80%		Power = 90%	
		Sample size per group	Overall 3 group sample size	Sample size per group	Overall 3 group sample size
sSOL (SD=33)	-6.8	371	1113	496	1488
	-7.6	300	900	398	1194
	-8	269	807	359	1077
	-8.7	229	687	300	900
	-9	213	639	284	852
	-10	172	516	230	690
	-11	143	429	191	573
sWASO (SD=43)	-9	360	1080	481	1443
	-9.9	300	900	398	1194
	-10	292	876	390	1170

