3 STATISTICAL METHODS

All statistical analyses will be performed by the sponsor or designee. When all subjects have completed Treatment Period 1 (Period 1), all data will be unblinded to the sponsor. There will be 3 database locks. The first will be of Period 1 data only, where data up to and including the visit at Month 6 will be analyzed. The second will include all data (Period 1 and ongoing Period 2 data) after all continuing subjects have completed the Month 9 (Period 2) visit, all available data will be analyzed to support regulatory submissions. The third will include all data where the study has continued to completion.

For the Period 1 analysis, sponsor staff and certain designees (detailed in the Study Integrity Charter) will be unblinded to the treatment allocation; however, subjects, investigators, and site personnel will remain blinded. These are not considered formal interim analyses since the primary and key secondary efficacy endpoints are all at Month 6 (Period 1), and there is no placebo control group in Period 2. Therefore, no Type I error adjustment is needed for efficacy analysis.

All descriptive statistics for continuous variables will be reported using number of observations (n), mean (arithmetic unless otherwise specified), standard deviation (SD), median, minimum and maximum. Categorical variables will be summarized as number and percentage of subjects. In summaries for safety the denominator for all percentages will be the number of subjects in a given treatment group. sSOL will be log transformed in analyses unless otherwise stated.

All statistical tests will be based on the 5% level of significance (two-sided).

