3.4.1 Primary Efficacy Analyses

The primary efficacy endpoint is the change from Study Baseline of sSOL at Month 6 of LEM10 and LEM5 compared to PBO.

Null Hypothesis: No difference exists in the mean change from Study Baseline to Month 6 of treatment with LEM10 (or LEM5) as compared with PBO.

Alternative Hypothesis: For sSOL, a difference exists in the mean change from Study Baseline to Month 6 for LEM10 (or LEM5) as compared with PBO.

The sSOL change from Study Baseline to Month 6 will be analyzed using the mixed effect model repeated measurement (MMRM) analysis on the FAS. The model will be adjusted for the corresponding Study Baseline value, region (North America, Europe and New Zealand, Asia), age group (<65 years old, ≥65 years old), treatment, time (1st 7 nights, Month 1, Month 2, Month 3, Month 4, Month 5 and Month 6) and the interaction of treatment by time. Since the sSOL is known to be non-normally distributed, a log-transformation will be used in the analysis.

The unstructured covariance matrix (UN) will be used in the analysis. In the case of non-convergence of UN, the toeplitz covariance matrix (TOEP) will be used. In the case of non-convergence with TOEP, the autoregressive covariance matrix [AR (1)] will be used in the model.

Before the implementation of the MMRM model, the missing values will be imputed using a pattern mixture model utilizing multiple imputation (MI) assuming the missing values are missing not at random (MNAR) utilizing the complete case missing value pattern (CCMV - subjects who completed all primary efficacy assessments without missing values). The missing values for a given visit will be imputed using all available values including the retrieved measurement from the post-discontinuation data.

The treatment comparison will be performed using contrasts. The p-value, least square (LS) means and the 95% confidence interval (CI) for the treatment difference will also be provided.

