7 PROGRAMMING SPECIFICATIONS

The rules for programming derivations and dataset specifications are provided in separate documents.

The following sample SAS statement provides the framework for the MI method:

CONVERT DATASET INTO MONOTONE MISSING DATA PATTERN (IMPUTING ARBITRARY MISSING DATA):

```
PROC MI data=<dataset> nimpute=30 seed=2006 out=<dataset1>;
  VAR age BMI baseline... visit1-visit8;
  MCMC chain=multiple nbiter=500 niter=300 impute=monotone;
  BY treatment;
RUN;
```

IMPUTE MISSING VALUES:

```
PROC MI data=<dataset1> nimpute=1 seed=2006 out=<dataset2>;
  CLASS treatment sex race region;
  MONOTONE regression (/details);
  MNAR model (visit2-visit8/ modelobs=CCMV);
  VAR treatment age sex race region BMI baseline....;
  BY _imputation_;
RUN;
```

PERFORMING MMRM:

```
PROC MIXED data=<dataset2>;
  CLASS subject treatment agegrp visit;
  MODEL value=treatment agegrp region visit visit*treatment / ddfm=kr;
  REPEAT visit/sub=subject type=UN;
  LSMEANS visit*treatment/DIFF CL;

  BY _imputation_;
  ODS output estimates=<dataset3>;
RUN;
```

COMBINE RESULTS:

```
PROC MIANALYZE data=<dataset3>;
  MODELEFFECTS estimate;
  STDERR stderr;
RUN;
```

VARIABLE ORDER TO BE USED IN THE PROC MI PROCEDURES:**To Create Monotone Missing Data Pattern**

- sSOL: age, baseline BMI, baseline ISI, baseline log(mean sSOL), log(mean sSOL) at first 7 nights, log(mean sSOL) at Month 1, log(mean sSOL) at Month 2, log(mean sSOL) at Month 3, log(mean sSOL) at Month 4, log(mean sSOL) at Month 5, log(mean sSOL) at Month 6

- sSE: age, baseline BMI, baseline ISI, baseline mean sSE, mean sSE at first 7 nights, mean sSE at Month 1, mean sSE at Month 2, mean sSE at Month 3, mean sSE at Month 4, mean sSE at Month 5, mean sSE at Month 6
- sWASO: age, baseline BMI, baseline ISI, baseline mean sWASO, mean sWASO at first 7 nights, mean sWASO at Month 1, mean sWASO at Month 2, mean sWASO at Month 3, mean sWASO at Month 4, mean sWASO at Month 5, mean sWASO at Month 6
- sTST: age, baseline BMI, baseline ISI, baseline mean sTST, mean sTST at first 7 nights, mean sTST at Month 1, mean sTST at Month 2, mean sTST at Month 3, mean sTST at Month 4, mean sTST at Month 5, mean sTST at Month 6

To Impute Missing Values

- sSOL: treatment, sex, race, region + variables used to create monotone missing data pattern
- sSE: treatment, sex, race, region + variables used to create monotone missing data pattern

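### Month 6 values not retrieved after stopping drug are imputed from completers, which does not match the Table 4 estimand and may overstate the effect; no planned analysis estimates the off-drug alternative

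*SAP*

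**What the plan says.** The primary row of Table 4 (SAP 3.3.6) covers "all randomized subjects regardless of the treatment subjects actually received" and counts data collected after dropout. That is what is usually called a treatment-policy target, although the SAP does not use the term. The same row says of the complete-case missing value (CCMV) method that "this method assumes dropouts or subjects with missing values have similar treatment effect as the completers within the respective treatment group".

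Other parts of the plan bear on this:

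- **Donors.** Table 3 (SAP 3.3.5) defines completers by having no missing post-baseline assessment. Being on drug is not part of the definition.
- **Retrieved data.** SAP 3.4.1 says the imputation draws on what is available, "including the retrieved measurement from the post-discontinuation data". Protocol 9.5.5 encourages subjects who stop drug to keep up the diary and visits.
- **Code.** SAP Section 7 runs MCMC within each arm to fill intermittent gaps, then a monotone regression with "modelobs=CCMV". The predictors are treatment, demographics, region, BMI, ISI, and baseline and visit values of the endpoint. None marks whether the subject was on drug.
- **Expected gaps.** Under Protocol 9.4.7.2, a subject who starts another insomnia treatment must leave the study, and this still applies after study drug has been stopped (short acute use can be agreed).
- **Other analyses.** CCMV-7, MMRM under MAR, the completer analysis and the per-protocol analysis are planned. Tipping-point analyses worsen the imputed Month 6 values in the lemborexant arms only (SAP Section 7).

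**The concern.** Take a subject who stops lemborexant in Month 3 and gives no further diary. The stated target needs that subject's Month 6 sleep off drug. The primary method supplies the sleep predicted for someone in the same arm with a complete diary, and most such people can be expected to be on drug. The estimand row and the imputation rule therefore answer different questions for that subject.

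At stake is how the Month 6 estimate is read. The same imputation approach is used for sSOL, sSE and sWASO, so it sits under all six gatekeeping comparisons. If the estimate is reported as the effect regardless of treatment received, it may look larger than that effect is. CCMV-7, MAR, completer and per-protocol results would not show the gap, because they also rest on same-arm data.

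**Working it through.** **1. The plan's own figure.** SAP Section 2 says "the standard deviation of change from Study Baseline for sSOL was assumed to be 33 minutes" and, for a difference of −8.7 minutes with 300 per group, that the trial "had >90% power for comparing a dose of lemborexant with PBO". Alpha is 0.05 two-sided (SAP 3) and allocation 1:1:1 (Protocol 9.4.3).

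- n per group = 2 × (1.96 + 1.2816)² × 33² / 8.7², which rounds up to 303, against 300 stated.
- Standard error at 300 per group = 33 × √(2/300) = 2.69. Power = Φ(8.7/2.69 − 1.96) = 89.8%, against 90% in Table 2.

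The figure reproduces to within rounding. The sample size is not in question; −8.7 serves below only as an example of an on-drug effect.

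**2. Illustration of size.** Let u be the share of the lemborexant arm that is off drug with Month 6 not retrieved, and k the fraction of benefit kept off drug. The documents give neither, so both are assumptions. Also assume no retrieval, and placebo dropouts like placebo completers. Then:

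- CCMV targets about −8.7.
- Effect regardless of treatment = −8.7 × [(1 − u) + k × u].
- Overstatement = 1/[(1 − u) + k × u] − 1.

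| u | k = 0: effect | overstated by | k = 0.5: effect | overstated by |
|---|---|---|---|---|
| 10% | −7.83 | 0.87 min (11%) | −8.26 | 0.44 min (5%) |
| 20% | −6.96 | 1.74 min (25%) | −7.83 | 0.87 min (11%) |
| 30% | −6.09 | 2.61 min (43%) | −7.39 | 1.31 min (18%) |

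With k = 1 the overstatement is zero. For the k = 0 effects, power at 300 per arm would be 83%, 73% and 62%.

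**3. What retrieval does.** A simple two-visit simulation (minutes, 300 per arm, 1,500 repetitions, 20% of each arm stopping, full loss of benefit in the lemborexant arm, complete-case regression imputation) gave these estimates against a true −6.96:

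- 0% retrieved: −8.80
- 25% retrieved: −8.28
- 50% retrieved: −7.77

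Simulation noise is about 2.69/√1500 = 0.07. Retrieval shrinks the gap but does not close it.

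**4. Direction.** Let L be the completers' mean improvement minus the dropouts' in an arm. Bias in favour of lemborexant = u(LEM) × L(LEM) − u(PBO) × L(PBO). With 20% unretrieved in both arms and L(LEM) = 8.7:

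- L(PBO) = 0: 0.2 × 8.7 − 0 = +1.74 min (overstated)
- L(PBO) = 8.7: 1.74 − 1.74 = 0
- L(PBO) = 15: 1.74 − 3.00 = −1.26 min (understated)

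The sign depends on how placebo dropouts fare, which the documents do not tell us.

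**The case against.** The SAP discloses the completer assumption in Table 4 and never calls it cautious. Diary completion after stopping drug is encouraged, and the values obtained are used as outcomes. The tipping-point analyses worsen only imputed lemborexant values, for all three endpoints, and their shifts can run from partial to full loss of benefit. Placebo-based imputation is itself untestable, since it takes the benefit to be fully lost.

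Most of this stands, and it rules out three stronger readings.

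- A reader might infer that the primary estimate is biased toward lemborexant. The documents do not establish that. Lack of effect is a listed reason for discontinuation (Protocol 9.5.5), so poorly sleeping placebo dropouts imputed from better placebo completers are plausible, and step 4 shows the bias can then vanish or reverse.
- A reader might infer from "modelobs=CCMV" that retrieved dropouts contribute nothing unless their diaries are complete. That is not so. Their observed values are outcomes. The MCMC step uses them and fills intermittent gaps, so a retrieved dropout with a Month 6 value becomes a donor. Off-drug values recorded before a final gap are predictors of that subject's own imputed values.
- A reader might take the 50% discontinuation figure in SAP Section 2 as the share affected. It is a worst case for safety exposure, and it counts stopping drug, not unretrieved diaries.

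What the objection does not answer is that the tipping-point runs look for the shift at which significance is lost. They name no plausible shift and give no estimate with off-drug outcomes for the unretrieved subjects. No other planned analysis does either.

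**Conclusion.** The mismatch is real and is in the SAP's own text. For values not retrieved after drug is stopped, the primary method targets a completer-like outcome, while Table 4 describes an effect regardless of treatment received. Overstatement is likely but not shown. It needs benefit to be lost off drug, and lemborexant dropouts to fall short of their completers by more, weighted by missingness, than placebo dropouts do.

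The 11%, 25% and 43% (or 5%, 11% and 18%) are correct arithmetic on assumed inputs. They are in minutes, whereas the primary analysis is on log(sSOL), and they allow for no retrieval. Nothing was computed for sSE or sWASO. The point calls for a supporting analysis and clearer wording. It does not show that the primary imputation must be replaced; moving the primary to a placebo-based rule would be a debatable trade-off.

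**What to change.** 1. **Named sensitivity analysis** for sSOL, sSE and sWASO, in SAP 3.4.1.3, 3.4.2.2 and Section 7. Split missing values by drug status at the visit, using the last-dose date that Protocol 9.3.3 already records, and state how a last dose inside the 7-night diary window is classed. Keep CCMV for on-drug gaps. Impute off-drug gaps from retrieved off-drug data in the same arm, or from the placebo arm if a prespecified minimum number of retrieved subjects is not reached.
2. **Tipping point.** State in advance the range of shifts regarded as plausible, on the scale of each endpoint, so that the tipping value can be judged against it.
3. **Table 4.** Reword the primary row to say that unretrieved values are assigned the completers' outcome, so that the CCMV estimate is not presented as the effect regardless of treatment received.

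The cost is SAP text, one more imputation program and a supporting estimate that may be less favourable. SAP Section 1 allows such changes if they are documented and approved before unblinding.

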3.4 Efficacy Analyses

Efficacy analyses for Treatment Period 1 will be performed on the FAS unless otherwise specified. Different baseline values will be used for endpoints defined during Treatment Period 1 (ie, Day 1 to Month 6) and during Treatment Period 2 (ie Month 7 to Month 12). Baseline values for each efficacy parameter are specified in [Section 6.1.1](#). The On-Treatment FAS will be used for the on treatment summaries produced by time on treatment.

Unless specified otherwise, all efficacy endpoints will be derived by calculating the average of weekly (7 days) diary parameter values ([Section 6.1](#)).

12-month LEM exposure data will be summarized by treatment (LEM5, LEM10) and duration of exposure (1 month [30 days], 3 months [90 days], 6 months [180 days], 9 months [270 days] and 12 months [365 days]). Treatment groups are LEM5 and LEM10, and include both (a) LEM Period 1 subjects on the On-Treatment Full Analysis Set using the change from Study Baseline and (b) LEM Period 2 subjects previously receiving PBO on the On-Treatment Full Analysis Set using the change from Period 2 Baseline. No hypothesis test will be performed for efficacy endpoints beyond the Month 6 visit.

The primary and key secondary endpoints comparisons are tested following the gate-keeping testing procedure described in [Section 3.3.3](#) to control for the overall type I error at the 0.05 significance level. The first primary efficacy endpoint comparison will be performed at the 0.05 significance level. The subsequent testings will only proceed if the previous test is statistically significant at the 0.05 level.

